# 3.2 End points:

- 1. Primary endpoints: Reduction in PBS total score by 3.7 points. This is in accordance with the MCID range reported by Chen et al, 2013 as 3.66-5.83 for PBS in children with neuromotor impairments.
- 2. For static balance: 1) reduction in the sway area of 95% confidence ellipse for center of pressure, 2) reduction in mediolateral direction of the postural sway.
- 3. For dynamic balance: Reduction in 1) step width, 2) double support period. Increase in 1) step length, 2) Cadence, 3) Gait velocity
- 4. Secondary endpoints: Safety.

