# 3. Intervention/ session 2-7:

Session 2 will occur 3-5 days after the baseline assessment.

3.1: Intervention group: Participants will choose 2 interactive video games on the Nintendo Switch Sports from golf, Frisbee, beach tennis, soccer, Volleyball, badminton, bowling, and chambara. The researcher will supervise the sessions via zoom. These games address motor learning principles as follows. First, they cause movement of the body's center of pressure in mediolateral, anteroposterior-, and diagonal directions without the participant paying active attention to the directional changes, leading to implicit and explicit learning. Second, they display the score achieved by the participant during- and after- each game leading to the participant having knowledge of the performance and the results. Third, playing 2 games provides task and training variability.

Games will be played for 10 minutes each with a 5-minute break in between. The same 2 games will be played each session. Participants will stand at least 3 meters away from the TV while playing the games. Verbal prompts /motivators will be provided during the games. Each session will take approximately 40 minutes. The caregivers will be present at one-hands distance from the participant to prevent any falls. Additionally, participants will be asked to place a chair at a reachable distance which they can hold on to prevent falls. Ideally, each session will occur with an off day in between, however this may not be realistic depending on participant and caregiver schedules and so sessions will occur at participant/caregiver convenience.

Control group: Control group participants will receive balance instruction from the researcher at home via Zoom. The following standard balance exercises will be performed for 15 minutes with 5 minutes of warm and cool down each. Breaks will be given as per the participants' need and verbal prompts/motivators provided. The caregivers will be present at one-hands distance from the

participant to prevent any falls. Additionally, participants will be asked to place a chair at a reachable distance which they can hold on to prevent falls.

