## 4. Post-intervention/session 8 and 9:

Static and dynamic balance will be reassessed as previously described to examine retention effects of the VR active gaming intervention (see study calendar). Session 8 will be at least 3-5 days after session 7. Parent/caregiver will return the Nintendo Switch Sports to the researcher. Session 9 will be 4 weeks after session 7. Each session will be for approximately 60 minutes.

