# 9.0 Reportable Events

Any event that requires prompt reporting to the IU IRB per the IU HRPP Policy on Reportable Events will be reported within five business days in compliance the IU HRPP Policy. Minor noncompliance and minor protocol deviations not meeting the requirements for prompt reporting will be reported at time of protocol renewal.

For questions about the rights as a research participant, to discuss problems, complaints, or concerns about a research study, or to obtain information or to offer input, please contact the IU

(Indiana University) Human Research Protection Program office at [contact] or at [contact].

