# 10.0 Study Withdrawal/Discontinuation

After reviewing the consent and/or assent form and having their questions answered, participants may decide to sign the forms and participate in the study. Or they may choose not to participate in the study. The decision is up to the participants. If they choose not to participate in this study or change their mind after signing the consent document, it will not affect their usual medical care or treatment or relationship with Indiana University.

If participants change their mind and decide to leave the study in the future, the study team will help them withdraw from the study safely. If they decide to withdraw, they should contact one of the a researchers to make them aware. Researchers will instruct the participant to stop playing the Nintendo Switch Sports and the researcher will collect the gaming console from the participant.

The researchers may stop the participation in the study even if participant do not want to stop if there is any incidence which leads to participant acquiring any exclusion criteria of this study such as any neurological or orthopedic condition affecting balance, epilepsy, or any type of injury that prevents you from continuing your participation during the data collection process of the study.

The PI will be responsible for data and safety monitoring. The study team will meet at least biweekly to discuss any difficulties while conducting the experimental protocols and review the data. [name] will always be available online when data collection is occurring. Minutes of each of the meetings will be maintained on the designated One-Drive folder for the Physical Activity Research lab.

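### Safety is the declared secondary endpoint, but the protocol defines no safety variable, schedules no event enquiry and plans no safety summary

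*Combined protocol and SAP*

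**What the plan says.** Section 3.2 closes its list of endpoints with "Secondary endpoints: Safety". No event type, time window, population or summary follows.

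Four other parts of the protocol bear on safety:

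- **Section 7.0, sessions 2 to 7.** For the gaming arm, "The researcher will supervise the sessions via zoom". For the control arm, "Control group participants will receive balance instruction from the researcher at home via Zoom". Both arms have the same precautions: "The caregivers will be present at one-hands distance from the participant to prevent any falls", and "participants will be asked to place a chair at a reachable distance which they can hold on to prevent falls".
- **Section 7.0, sessions 8 and 9.** "Static and dynamic balance will be reassessed as previously described to examine retention effects". Nothing else is assessed at these visits.
- **Section 9.0.** "Any event that requires prompt reporting to the IU IRB per the IU HRPP Policy on Reportable Events will be reported" within five business days. The sentence after it concerns minor noncompliance and protocol deviations, not minor harms.
- **Section 10.0 (withdrawal).** The PI is responsible for data and safety monitoring, and a team member is available online during data collection. "The study team will meet at least biweekly to discuss any difficulties while conducting the experimental protocols and review the data", and minutes are kept. Researchers may end participation when someone acquires an exclusion condition or an injury that prevents them from continuing.

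The table of contents lists a Data Safety Monitoring section as 10.0. The body has no section with that title, only the short text under Study Withdrawal/Discontinuation.

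**The concern.** An endpoint needs a variable, a time at which it is collected, and an analysis. Here the endpoint has a name and none of the three.

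The protocol itself foresees the relevant harms. It guards against falls with a caregiver and a chair. Section 4.2 excludes people with pain, dizziness or conditions that a screen can worsen. The screening questionnaire asks about such symptoms (Q5 to Q7) and about balance difficulties, including frequent falls (Q10). It does so once, before session 1, and no later visit is told to ask again. The withdrawal rule in section 10.0 likewise depends on learning of a newly acquired condition that no session asks about.

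At stake is what the final report can say. Section 4.2 states that no VR sickness is expected and that no other harms are reported for this duration. With that prior view and no active enquiry, a short list of events could be taken as confirmation when it may only reflect that nobody asked. Events that were not collected cannot be recovered at the analysis stage.

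**Working it through.** The plan gives no figure for safety, so there is none to reproduce. Its sample size (14 per group) concerns the balance outcomes and has no bearing here.

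**Step 1. Look for the endpoint wherever it could be made operational.**

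| Place | What it contains | Safety variable, enquiry or summary |
|---|---|---|
| 3.1 Outcome measures | Pressure mat, motion capture, PBS | None |
| 7.0, session 1 | Familiarization, demographics, baseline balance and gait | None |
| 7.0, sessions 2 to 7 | Training over Zoom, fall precautions | Precautions only; no instruction to record a fall |
| 7.0, sessions 8 and 9 | Balance reassessment | None |
| 8.0 Study Calendar | The same items by session | None |
| 11.0 Statistical Considerations | Sway, gait and PBS as dependent variables | None |

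The abbreviations list has entries for adverse event and serious adverse event, but no section of the supplied body uses either term.

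**Step 2. List what would become known anyway.** There are four routes: IRB-reportable events (9.0), injuries that end participation (10.0), difficulties raised in minuted meetings (10.0), and events seen live over Zoom (7.0). All are unsolicited. The first two have a threshold, so a minor fall, strain or passing dizziness need not reach them. The fourth works only while a session is running, and the researcher's role differs between arms (supervising play, or leading exercises), so detection need not be equal.

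**Step 3. Count the contacts.** Sessions 2 to 9 are 8 contacts per participant. 40 × 8 = 320 planned contacts if everyone attends (fewer with the attrition that section 11.0 expects), none with a scheduled safety question. Session 9 is 4 weeks (28 days) after session 7. If session 8 falls 3 to 5 days after session 7, the gap between sessions 8 and 9 is 28 − 5 = 23 to 28 − 3 = 25 days, with no contact described.

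**Step 4. Check who would be counted.** Section 11.0 says that data from people who took part in every intervention session enter the analysis. It also announces intention to treat for the balance outcomes. Take an assumed case: 1 of 20 in an arm stops after an injury and the other 19 complete. Counting everyone who started gives 1/20 = 5%. Counting completers gives 0/19 = 0%.

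**Step 5. What complete collection could show.** At 20 per arm with zero events, the exact upper limit is 1 − 0.025^(1/20) = 16.8% (two-sided 95%), or 1 − 0.05^(1/20) = 13.9% (one-sided 95%). The documents give no event risk, so the risks below are assumptions. The chance of at least one event in 20 is 1 − (1 − p)^20:

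| Assumed risk p | Chance of at least one event |
|---|---|
| 1% | 18% |
| 5% | 64% |
| 10% | 88% |
| 20% | 99% |

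These limits follow from 20 participants per arm and would apply to a trial with perfect collection. They show why the safety report should be descriptive. They do not measure the gap found in step 1.

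**The case against.** The strongest reply is that this is a low-risk intervention with reasonable oversight. The device is hand-held and play lasts 20 minutes. A caregiver stands within reach, a researcher is on every training call, a team member is available online during data collection, and the PI holds responsibility for safety. A small study may fairly rely on that together with the institutional reporting policy, and how often to ask is partly a matter of judgement.

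Much of this stands, and it rules out several stronger readings:

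- A reader might infer that the trial will have no safety data at all, or that the IRB is the only route. Sections 7.0, 9.0 and 10.0 contradict both.
- A reader might infer that a participant could finish the whole course between two team meetings. That takes biweekly to mean every two weeks, ignores that it is a minimum, and assumes three sessions a week although section 7.0 lets sessions follow the family's convenience. It also overlooks the live supervision.
- A reader might infer that the sponsor plans to declare the games safe. No section says so.
- A reader might infer that no event form exists. Some appendix items are not in the supplied text, so a form cannot be ruled out. No visible section refers to one.

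What does not stand is the step from monitoring to endpoint. Oversight protects participants. It does not yield a defined quantity collected in the same way in both arms.

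**Conclusion.** The point holds in this form: safety is declared an endpoint without a defined variable, a scheduled enquiry or a planned summary. Following the visible plan exactly would give an incomplete set of unsolicited reports and no comparable count per arm. The completer statement in section 11.0, if applied to safety, could also drop the people who matter most.

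The extent is every planned contact after baseline, up to 320 if all 40 participants attend. How many events would be missed cannot be estimated, because the documents give no event rate. The conclusion assumes that no appendix item outside the supplied text contains a safety form.

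This should be corrected before data collection, because it cannot be repaired afterwards. It does not affect the primary balance comparison.

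**What to change.** 1. **Section 3.2.** Define the endpoint as the number of participants with an event and the number of events, per arm, from the start of session 2 to session 9. Cover falls, near-falls needing caregiver or chair contact, new pain or injury, dizziness, seizure, and sessions stopped early.
2. **Section 8.0.** Add one row to the calendar. At sessions 2 to 9 the researcher already present asks, in identical words in both arms, whether any of these has occurred since the last contact, and logs any seen during the session. Answers at the start of session 2 concern the time before training and serve as a baseline. Screening items Q5 to Q7 and Q10 should not simply be reused. Q5 to Q7 ask about current conditions and Q10 about perceived balance difficulties, so an event that came and went between contacts would be missed.
3. **Section 11.0.** Summarise counts by arm, with exact confidence intervals for the proportion of participants affected, in everyone who started at least one session and not only completers. State that no claim of demonstrated safety will be made.
4. **Section 10.0.** The sponsor should reconcile how session-level reports reach the PI with the monitoring and withdrawal text, and with the Data Safety Monitoring section named in the contents.

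The cost is protocol wording, a short checklist and about two minutes at each existing contact, with no new visits or staff. Recorded event counts will be higher than under spontaneous reporting, and the report should say so.

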# 4.0 Eligibility Criteria

#### 4.1 Inclusion Criteria

- a) age 7-22 years,
- b) existing ASD DSM-5 level 1 or 2 diagnosis confirmed by medical record/ educational services categorized under ASD/ therapeutic services categorized under ASD/ any other official document indicating the diagnosis of ASD,
- c) able to follow instructions and
- d) able to stand unsupported for at least 20 minutes.

#### 4.2 Exclusion Criteria

- a) epilepsy or other medical conditions which can be exacerbated by looking at a screen,
- b) Uncorrected vision loss or any other eye condition prohibiting looking at the screen for a prolong time,

c) co-occurring musculoskeletal conditions such as joint or muscle pain or stiffness that limits mobility, implanted plates, pins, or screws that limit mobility, fractures or recent surgeries or any other physical condition that could interfere with the ability to play an active video game d) co-occurring neurological conditions such as numbness or muscle weakness, temporary loss of vision, speech or strength, loss of consciousness (black out), Dizziness or lightheadedness, Impaired memory or confusion, any other cooccurring diagnosis that could be negatively impacted by playing an active video game

e) any other health conditions that are contraindicated to or may interfere with physical activity such as impaired hearing (uncorrected), medically documented balance disorder, Any heart condition prohibiting exercise, chronic pain or any pain at the time of testing, need assistance to stand for 20 minutes or more,

[figure not shown]
f) aggression or other severe behaviors that may limit the ability to safely participate in the intervention.

As participants in the intervention group will be using hand-held and not a head-mounted device for VR active video gaming, we are not anticipating any VR sickness. There are no other VR/ active gaming related issues reported in the literature which can negatively impact participants' health due to 20-minute intervention duration.

# 5.0 Study Design

Single blinded randomized controlled clinical trial design will be used. After obtaining the consent material, potential participants will be screened using inclusion and exclusion criteria, ASSQ and screening questionnaire. Co-PI will create and administer the assignments. Participants will be blinded to the allocation process to either the intervention or the control group.

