3. Pediatric Balance Scale (PBS): The PBS will be used to assess static and dynamic balance. It is a valid and reliable clinical balance assessment tool for children and youth with motor impairments. It is a 14-component battery that evaluates daily living tasks such as sitting to standing, transferring from one chair to another, and sitting and standing without support. Item numbers 1-3 and 9-14 are specific to dynamic balance while item numbers 4-8 are specific to the static balance. Participants are graded as 0-4 on each component of the scale with 56 being the highest total score achieved. A higher score indicates better postural control. Interpretation of the scores is as follows: 41 to 56 denotes a low fall risk, 21 to 40 a medium fall risk, and 0 to 20 a high fall risk. The PBS takes fifteen to twenty minutes to administer. A different researcher from the study team will record the PBS to

avoid any assessment bias. The researcher will demonstrate each task and the participant will be allowed 1-2 practice trials before official assessment as per the instructions provided in the tool. The researcher is well trained in administrating the PBS. Inter- and Intra-rater reliability will be checked at least four times throughout the course of the study by scoring a videotaped administration of the tool. An intraclass correlation of 0.9 must be achieved to avoid retraining on the PBS.

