# 2. Pre-intervention/session 1:

2.1 As part of familiarization, participants will be shown and allowed to handle the different data collection instruments and ask questions. The intervention group will be shown the Nintendo Switch to get familiarized with their operation and functions. Parents/caregivers of the participants (under 18 years of age) in the intervention group will be handed over the Nintendo Switch Sports

to be connected at their home for the duration of intervention. Participants 18 years of age or older will be given the device. Researchers will provide any technological assistance required for this purpose.

2.2 Weight will be recorded using a calibrated scale and height measured using a stadiometer. The Edinburgh Handedness Inventory-short form (EHI-SF) will be used to assess hand-preference. It is a valid and reliable 4-item checklist of everyday tasks and participants score their hand preference on 5-point Likert scale (for each item, always right= 100, usually right= 50, usually left= 50, always left= -100). A researcher will read the rating scale to those with low literacy level. Handedness will be determined using a laterality quotient. The laterality quotient is interpreted as left handers (-100 to -61), mixed handers (-60 to +60) and right handers (61 to 100). Hand length will be calculated using a tape cloth, measured from greater tuberosity to distal end of middle digit on the right hand and leg length iliac crest to ground on the right leg.

Participants will be shown the different data collection instruments to handle, get familiarized and ask questions. Participant's hand dominance will be recorded using the Edinberg Handedness Inventory-short form. Participant's foot dominance will be recorded by asking them to kick an imaginary ball placed on the ground in front of them. Practice trials for balance and gait assessments will be conducted to ensure understanding of the protocol. Baseline assessments for posture and gait will be performed.

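### The trial is labelled single blinded, but no one is stated to be blind to treatment, and the separate rater of the PBS primary endpoint is not said to be masked to arm

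*Combined protocol and SAP*

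**What the plan says.** Section 5.0 states: "Single blinded randomized controlled clinical trial design will be used". The only blinded party it names is the participants: "Participants will be blinded to the allocation process to either the intervention or the control group". It also says: "Co-PI will create and administer the assignments".

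Under section 7.0, item 2.1 (session 1): "The intervention group will be shown the Nintendo Switch to get familiarized with their operation and functions". The console is then handed to the caregivers of minors in that arm, and for adults: "Participants 18 years of age or older will be given the device". For the other arm, item 3 of section 7.0 says: "Control group participants will receive balance instruction from the researcher at home via Zoom".

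Section 3.2 labels a 3.7-point change in PBS total as the primary endpoint. Section 3.1 describes the PBS as 14 observer-graded items scored 0-4, maximum 56. On who scores it, section 3.1 says "A different researcher from the study team will record the PBS to" prevent assessment bias. It adds rater training, and reliability checks on video at least four times with an intraclass correlation threshold of 0.9.

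In the post-intervention text of section 7.0, which covers sessions 8 and 9: "Parent/caregiver will return the Nintendo Switch Sports to the researcher". Section 10.0 has the study team meeting at least every two weeks and reviewing data.

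**The concern.** A blinding label tells the reader which source of bias has been controlled. Here it is attached to participants, who see which treatment they get. The role for which masking is both feasible and useful is the PBS rater, and on that role the text is silent.

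The PBS depends on human judgement twice over. The researcher demonstrates each task and allows practice trials, then grades the performance. Both hypotheses in section 2.1 are directional in favour of gaming. A rater who knows the arm and shares that expectation could administer or grade the scale differently by arm. That error would look like a treatment effect, and a larger sample would not remove it.

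**Working it through.** **1. The plan's own figure.** The plan gives no number for blinding. The nearest figure is the sample size in section 11.0: f = 0.25, alpha 0.05, power 0.80, 14 per group. I took 2 groups and 3 assessments (sessions 1, 8, 9). A correlation of 0.5 between assessments and sphericity are my assumptions, since the plan states neither.

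- λ = f² × N × m / (1 − ρ) = 0.0625 × 28 × 3 / 0.5 = 10.5, with 2 and 52 degrees of freedom: power 0.812. The 14 per group reproduces for the time effect and for the group-by-time interaction.
- With all 40 recruited: λ = 0.0625 × 40 × 3 / 0.5 = 15, with 2 and 76 degrees of freedom: power 0.935.

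Masking does not enter this calculation, so the fix leaves the sample size as it is.

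**2. Who is stated to be blind to treatment.**

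| Role | What the documents say | Blind to treatment? |
|---|---|---|
| Participants and caregivers | Blinded to the allocation process (5.0); given a console or live exercise instruction (7.0) | No, by the nature of the treatments |
| Co-PI | Creates and administers assignments (5.0) | No |
| Researchers supervising sessions | Gaming or exercise over Zoom (7.0, item 3) | No |
| PBS rater | A different researcher, to prevent bias (3.1) | Not stated |
| Sway and gait assessors, analyst | No masking described | Not stated |

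**3. How the arm can become visible to the rater.**

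- Session 1: console familiarisation and hand-over are item 2.1; baseline measurement follows in items 2.2 to 2.4.
- Session 8: the console's return is written into the same paragraph as the reassessment.
- Between visits: the rater belongs to the study team, which reviews data at least every two weeks (10.0).
- Allocation: after a coin flip, the next participant in the same age range goes to the other group (6.0). Anyone who knows the first arm knows the next.

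For session 9 the text shows no route specific to that visit; knowledge gained earlier would carry over.

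**4. Size on the PBS scale (illustration).** One grade on one item is 1 point. The 3.7 points serve only as a yardstick of size.

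- 1 / 3.7 = 0.27
- 2 / 3.7 = 0.54
- 4 points exceed 3.7

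These fractions apply to the group contrast only if the shift is the average difference between arms. A shift that is equal at every visit cancels in the group-by-time interaction. A shift that differs between baseline and follow-up does not.

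**5. Effect on the false-positive rate (illustration).** The documents give neither a PBS standard deviation (SD) nor a bias size, so the shift b is in SD units over an assumed range. Inputs are no true effect, 20 per arm (6.0) and two-sided alpha 0.05.

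- Two-group comparison at one visit, normal approximation: SE = √(2/20) = 0.316 SD; rate = Φ(−1.96 − b/SE) + 1 − Φ(1.96 − b/SE). For b = 0.2, b/SE = 0.632 and the rate is 0.097.
- Interaction, with shift 0 at baseline and b at both later visits, correlation 0.5: the squared centred half-differences sum to b²/6, so λ = 40 × (b²/6) / 0.5 = 13.33 b², with 2 and 76 degrees of freedom.

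| Shift b (SD) | Two-group comparison | Interaction |
|---|---|---|
| 0 | 5.0% | 5.0% |
| 0.1 | 6.2% | 6.0% |
| 0.2 | 9.7% | 9.1% |
| 0.3 | 15.8% | 14.7% |
| 0.5 | 35.3% | 34.1% |

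**The case against.** A reader might infer four stronger claims that the documents do not support.

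- *The protocol falsely claims that participants are blind to treatment.* Its words concern the allocation process, which can mean only that the sequence is concealed. On that reading there is no false claim about treatment, but then no one at all is stated to be blind to it, and the label has no content.
- *The PBS rater is unblinded.* The text is silent. A separate rater is assigned expressly to limit bias and may be masked in practice. The flow diagram and some pages are not available.
- *The arm is visible to the rater at baseline and at session 8.* Nothing places the PBS rater at the console demonstration or makes that person the one who takes the console back. List order need not be strict time order. The text shows possible exposure only.
- *All primary outcomes depend on an unmasked rater.* Section 3.1 also lists the pressure mat and motion capture as primary measures. These are instrument-based and less exposed, although staff give balance support and verbal prompts.

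It is also fair that the rater is trained and checked against an intraclass correlation of 0.9, which limits gross scoring drift. But agreement is not masking: two raters who both know the arm can agree and share the same bias.

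**Conclusion.** The point stands in this form: the protocol states a blinding property that its procedures do not give to anyone with respect to treatment, and it does not state masking for the one observer whose judgement determines the labelled primary endpoint. This rests on the text alone and needs no assumption about how the rater works in practice.

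The size of any resulting bias is unknown. The 27-54% assumes an average differential shift of 1-2 points. The false-positive rates assume a shift of 0.1 to 0.5 SD and, for the interaction, a correlation of 0.5. Both show what is at stake and do not estimate bias in this trial. The sponsor should correct this, because the remedy is specific and builds on a rater already planned.

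**What to change.** - State that the PBS researcher in section 3.1 is kept unaware of arm at sessions 1, 8 and 9, and takes no part in allocation, Zoom sessions, console handling or the parts of team meetings that identify arm.
- In session 1, move both the console demonstration and the hand-over to after the baseline assessments. Moving the hand-over alone would leave the demonstration in view.
- At session 8, have another existing team member receive the console, away from the PBS assessment.
- Ask participants and caregivers not to reveal their arm to the rater.
- Process mat and gait files under coded IDs.
- In section 5.0, describe the trial as assessor-blinded for PBS and remove the implication that participants are blinded.

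Cost: a re-ordered session 1, wording of staff roles, and coded file names. Staffing on assessment days becomes less flexible. The documents give no staff numbers, so some roles would need reassigning if the PBS researcher currently also supervises Zoom sessions. The 14 per group and the 40 recruited stay as they are.
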